### **9.5.1 Exposure to Study Medication and Compliance**

NA.

### **9.5.2 Interim Analysis for Safety**

NA.

### **9.5.3 Adverse Events**

This protocol uses the definition of adverse event from 21 CFR 312.32 (a): any untoward medical occurrence associated with the use of an intervention in humans, whether or not considered intervention-related.

For this study a serious adverse event includes, as outlined at: <https://www.hhs.gov/ohrp/regulations-and-policy/guidance/reviewing-unanticipated-problems/index.html>:

1. results in death;
2. is life-threatening (places the subject at immediate risk of death from the event as it occurred);
3. results in inpatient hospitalization or prolongation of existing hospitalization;
4. results in a persistent or significant disability/incapacity;
5. results in a congenital anomaly/birth defect; or
6. based upon appropriate medical judgment, may jeopardize the subject's health and may require medical or surgical intervention to prevent one of the other outcomes listed in this definition (examples of such events include allergic bronchospasm requiring intensive treatment in the emergency room or at home, blood dyscrasias or convulsions that do not result in inpatient hospitalization, or the development of drug dependency or drug abuse)

## **9.6 Sample Size Justification**

For our primary outcome, percent change in weight at 24 months, we have calculated sample size based on a two-sided test of significance with  $\alpha=0.05$  and the standard deviation (SD) of percent change in weight of 7.3% as observed in the Heart Health Lenoir Project. Table 5 illustrates sample size calculations (allowing for 20% attrition) for various differences in mean changes between study groups based on a 1:1 randomization allocation ratio. This table also provides power calculations to detect differences in weight change compared to augmented usual care separately for pre-specified subgroups (those with vs. without diabetes, female vs. male, and white vs. African American assuming no sub-group is less than 40% of the overall sample). We expect the intervention to reduce weight by at least 5% and that average weight loss in the intervention group will exceed that in augmented usual care by at least 4% (we estimate weight loss in usual care of  $\leq 1\%$ ). Our plan to enroll 360 participants provides excellent power for our primary outcome

(>99%) and reasonable power (82%) within each of our pre-specified sub-groups. For a difference between groups as small as 3%, we still have robust power for our primary outcome. Although we do not anticipate major differences in weight loss between those in our pre-specified subgroups, we will test the potential for large differential effects between subgroups using interaction terms. However, under the assumptions described above, our power to detect realistic difference in effects of 2-3% between these subgroups will be limited (about 20-40%). Also, for a difference in proportions of those losing  $\geq$  5% body weight as small as 15% (e.g., 15% control vs. 30% intervention), allowing for attrition, the proposed sample size provides 85% power. For several secondary outcomes, we present in Table 5 minimally detectable differences corresponding to effect size of 0.33 for the sample size of 360 with 20% attrition, 80% power, and  $\alpha = 0.05$ .

Note, the table below assume sample size of 350. After funding, the investigative team elected to increase sample size to 360 with a goal of 120 participants per wave.

| Table 5. Power Estimates for % Change in Weight at 24 Month Follow-up |                   |                                    |   |
|--|-------------------|------------------------------------|---|
| Assumed Mean % Change Difference Between Groups                              | Total Sample Size | Overall Power to Detect Difference | Minimum Power within Each Subpopulation (Diabetes status, sex, and race) to Detect Specified Difference |
| 3%   | 300               | 0.89                               | 0.51  |
|  | 350               | 0.93                               | 0.58  |
|  | 400               | 0.96                               | 0.64  |
| 4%   | 300               | 0.99                               | 0.76  |
|  | 350               | 0.99                               | 0.82  |
|  | 400               | 0.99                               | 0.87  |

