3.2c. Control group considerations: Current evidence suggests “usual care” dietary interventions in primary care settings are either absent (only 20% of patients with CVD, diabetes, or dyslipidemia receive clinic-based nutrition counseling),⁷⁷ ineffective,⁵ or minimally effective (1.2 kg weight loss at 24 months).³ However, given Task Force recommendations and ethical considerations for patients who enroll in a weight loss study, control participants will be offered a weight loss program of an intensity consistent with Task Force guidelines (WW™). It will be given free of charge, similar to the experience of the intervention group. Given prior success of weight loss interventions given in primary care settings^{3,5} and by commercial programs,⁴ we anticipate weight loss at 24 months in our control group will not exceed 1.0% of initial body weight. As noted by Wadden,⁵ weight loss in the control groups of studies conducted in primary care was typically < 0.5%, even among control participants who received augmented usual care.⁷⁸ As we recognize there will be some overlap in dietary pattern between intervention and control groups, we propose objective (skin carotenoids) and rigorous self-reported measures of dietary intake in both groups to assess the degree of overlap.

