Overall, among participants with diabetes, the mean percent weight change at 24 months was -3.6% (-5.0 to -2.0). In addition, 33% of participants with diabetes maintained 5% weight loss and 20% maintained 7.5% weight loss at 24 months. Ninety percent of those in the weight loss program were satisfied or very satisfied with the program. Importantly, among those in the lifestyle only group, weight loss was -3.8 kg (-5.9 to -1.8) at 24 months, suggesting a change in dietary pattern may have led to weight loss⁷⁵ without an explicit intervention to lose weight. A possible explanation for weight loss in this group, as compared to PREDIMED participants who on average lost minimal weight,⁴⁸ is difference in baseline diet, with more poor quality carbohydrates and processed food in the American diet compared to the European diet¹⁰³ and particularly so in the southeastern United States.¹⁰⁴⁻¹⁰⁷ In this setting of excess poor quality carbohydrate intake, a change to a Med-style, unrestricted high-quality fat diet may have positive metabolic and appetite suppressing effects.^{62, 63, 65} A major limitation of HHL weight loss outcomes was the pre-post study design, though weight loss over time is not commonly observed for adults and there were no secular trends suggesting weight loss in NC during the time of this study.¹⁰⁸ Also, the weight loss trajectory among participants with diabetes in HHL was different from most weight loss studies—weight loss improved over time, instead of the usual rapid weight loss over 6 months with attenuation of weight loss typically seen at 12 and 24 months.¹⁰⁹ This trajectory of weight loss may be clinically important in light of increased CVD risk reported for those with weight fluctuations.¹¹⁰

Among participants without diabetes in HHL, weight loss was 0.4 kg (-1.4, 0.6) at 24 months. There are several reasons why those without diabetes may have had less weight loss. On average, they weighed 8 kg (103 vs. 95) less at baseline⁷⁵ and the majority (54%) did not choose to be in the weight loss intervention. Thus, they may have had a lower level of motivation to lose weight than those with diabetes. Furthermore, both short- and long-term weight loss has been shown to be greater when the trigger for weight loss is medical in nature.¹¹¹

3.3a. Phase I (4 months), lifestyle phase:

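### The 85% power stated for a 15-point responder difference depends on an unsourced 15% control rate that does not fit the plan's own control mean and SD; under those assumptions power is about 75% to 84%

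*SAP*

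**What the plan says.** SAP 9.6 gives a power figure for the responder endpoint, the proportion losing at least 5% of "body weight as small as 15% (e.g., 15% control vs. 30% intervention), allowing for attrition, the proposed sample size provides 85% power". Protocol 9.2 and 9.4.7 carry the same sentence. The rates are offered as an example, and neither document gives a source for the 15%.

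The same SAP paragraph assumes "the standard deviation (SD) of percent change in weight of 7.3% as observed in the Heart Health Lenoir Project". It puts usual-care loss at 1% or less and says "We expect the intervention to reduce weight by at least 5% and that average weight loss in the intervention group will exceed" that in usual care by at least 4 points. Protocol 4.2 agrees on the control arm: "we anticipate weight loss at 24 months in our control group will not exceed 1.0% of initial body weight". It adds that primary-care control groups typically lost under 0.5%.

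The preliminary data in Protocol 6.1.1 (section 3.1b) report that, at a mean loss of 3.6% at 24 months, "33% of participants with diabetes maintained 5% weight loss".

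**The concern.** For a fixed 15-point difference, power falls as the control rate rises towards 50%. A low assumed control rate therefore gives a favourable figure. The paragraph sets out a control mean and an SD, then quotes responder power at a control rate that those two figures do not readily produce.

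The proportion losing at least 5% is the first secondary weight objective listed. The sentence presents 15 points as a difference the trial can detect with 85% power, and a reader would use that figure to judge a null or borderline responder result. If the true control rate is nearer 20% to 30%, the trial is less able to detect 15 points than stated.

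**Working it through.** **Inputs.**
- Two-sided 5% test, 1:1 allocation and 20% attrition (SAP 9.6: "illustrates sample size calculations (allowing for 20% attrition"). These are stated for the primary outcome and assumed here to carry over to the responder figure.
- Evaluable per arm: 360 × 0.8 / 2 = 144 now, and 350 × 0.8 / 2 = 140 for the sample size the text was written for.
- SD 7.3, control mean loss 0 to 1%, intervention mean loss 5%.

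**Power formula** (two-proportion z-test, pooled null variance, no continuity correction), with p̄ the mean of p1 and p2:

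power = Φ{ [ |p2 − p1| − 1.96 √(2p̄(1 − p̄)/n) ] / √(p1(1 − p1)/n + p2(1 − p2)/n) }

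**Step 1: reproduce the stated figure.** For 15% vs 30%, p̄ = 0.225.
- n = 140: (0.15 − 1.96 × 0.0499) / 0.0491 = 1.063, so power is 85.6%.
- n = 144: (0.15 − 1.96 × 0.0492) / 0.0484 = 1.106, so power is 86.6%.

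The 85% is reproduced.

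**Step 2: control rate under a normal approximation (an assumption).** P(loss ≥ 5%) = Φ((m − 5)/7.3), where m is the mean loss in percent. At m = 1 this is Φ(−0.548) = 29.2%; at m = 0 it is Φ(−0.685) = 24.7%. Working backwards, a 15% control rate with SD 7.3 needs a mean gain of 1.036 × 7.3 − 5 = 2.6%. Alternatively, at a 1% mean loss, it needs an SD of 4/1.036 = 3.9.

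**Step 3: check the approximation on the prior study.** A mean loss of 3.6% with SD 7.3 predicts Φ(−1.4/7.3) = 42% losing at least 5%, but 33% is reported. The denominator is not stated. If it was all 124 participants with diabetes, 33% corresponds to 0.33 × 124 / 93 = 44% of the 93 (18 + 25 + 50) with 24-month weights in Protocol Table 2, close to the normal prediction. If it was the 93, normality over-predicts.

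To cover the second case, shift on the probit scale so that 33% is matched: Φ⁻¹(0.33) + 1.4/7.3 = −0.440 + 0.192 = −0.248. The calibrated control rate is Φ((m − 5)/7.3 − 0.248). The shift is also an assumption.

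**Step 4: power for 15 points at 144 per arm.**

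| Control mean loss | Normal: control rate | Power | Calibrated: control rate | Power |
|---|---|---|---|---|
| 0% | 24.7% | 78.1% | 17.5% | 84.0% |
| 0.5% | 26.9% | 76.7% | 19.4% | 82.2% |
| 1% | 29.2% | 75.5% | 21.3% | 80.6% |

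The shortfall against 85% runs from 85 − 84.0 = 1.0 to 85 − 75.5 = 9.5 points.

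Without any distributional model, power for 15 points at 144 per arm by control rate is: 15%, 86.6%; 20%, 81.7%; 25%, 77.9%; 30%, 75.1%.

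**Step 5: the effect the plan expects (1% vs 5% mean loss), 144 per arm.**
- Normal: 29.2% vs Φ(0) = 50%, power 95.4%.
- Calibrated: 21.3% vs Φ(−0.248) = 40.2%, power 93.9%.

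**The case against.** The strongest reply is that nothing has been miscalculated. The 85% is correct for the rates shown, and those rates are labelled as an example. This stands: the problem lies in the input and in the general wording around it.

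Second, a mean and an SD do not determine a tail proportion, and no section says that weight change is normal. A reader might infer that the plan implies a 29% control rate and so contradicts itself. The documents do not support that. The 29% needs normality, which the prior-study figures can neither confirm nor rule out, and it needs a control loss of exactly 1%, which is the plan's ceiling. Nor is the control mean an input to the primary power tables, which use only the between-group difference and the SD.

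Third, the 30% intervention rate would correspond to a mean loss of about 1.2% under normality (5 − 0.524 × 7.3). That is no inconsistency, because the sentence describes a smaller effect than expected, as the 3% rows of the primary power table do.

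Fourth, a reader might push the control rate higher using the 2.2 loss that Protocol 2.2 cites for commercial programmes. That figure is in kilograms at 12 months and cannot stand in for percent loss at 24 months.

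Fifth, the practical stakes are limited. SAP 9.4.1 analyses this endpoint with a covariate-adjusted mixed logistic model, so no z-test figure is its exact power. SAP 6.2 and 6.6 expect under 5% missing weights once health-record weights are added. At 360 × 0.95 / 2 = 171 per arm, power for 15 points would be about 82% from a 29.2% control rate and 87% from 21.3%. This softens the point for that analysis, but the stated figure is explicitly one that allows for attrition, and the paragraph's allowance is 20%.

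**Conclusion.** The point holds in a limited form. The 85% is right for 15% vs 30%, but the 15% is unsourced and fits poorly with the paragraph's SD and its control loss of at most 1%. Over a control mean loss of 0 to 1%, with 144 evaluable per arm, power for 15 points is about 78% to 75% under normality and about 84% to 81% after calibration to the prior study. The general claim is therefore overstated by about 1 to 10 points. The range reflects assumptions the documents do not settle: the shape of the distribution, the denominator of the 33%, and where below 1% the control mean falls.

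A reader might infer that the responder endpoint is underpowered. It is not, for the effect the plan expects: power there is about 94% to 95% on either set of assumptions. The primary analysis is unaffected.

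**What to change.** Restate the sentence in SAP 9.6 and Protocol 9.2 and 9.4.7, in one of two ways.

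1. Give the source of the 15% control rate and limit the 85% to that rate.
2. State power for a 15-point difference across control rates of 15% to 30% (about 87% falling to 75% at 360 randomized with 20% attrition). Add the power at the rates implied by 1% vs 5% mean loss (about 95% under normality, 94% after calibration), and name the distributional assumption used to get from means to proportions.

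The second is more useful to someone interpreting the responder result. The cost is a few lines of text and a less favourable figure for 15 points. The SAP was drafted after all participants were randomized, and no change to sample size or analysis is needed.

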### Appendix A: Summary of Assessments

| Table 3: Outcomes/ Measures  | Collection Time (min) | Data collected times (months) |   |    |    | Comment   |
|---|-----------------------|-------------------------------|---|----|----|---|
|   |                       | 0                             | 4 | 12 | 24 |   |
| Weight (primary outcome) , by electronic scale as the average of two measures, and height (baseline only). SECA 874 dr scales will be used and assessed monthly for accuracy with standardized weights.. | 5                     | x                             | x | x  | x  | At study outset, seven standardized 50 lb. weights certified for accuracy by NC state standards lab.*   |
| Secondary Outcomes   |                       |                               |   |    |    |   |
| Objective measures  |                       |                               |   |    |    |   |
| --Blood pressure by noninvasive automated monitor (Omron HEM-907XL, Vernon Hills, IL) with a first measure after seated for 5 minutes and 2 repeat measures at 1-minute intervals                               | 10                    | x                             | x | x  | x  |   |
| --Blood work: Non-fasting total & HDL cholesterol, A1c , interleukin (IL)-6 , tumor necrosis factor (TNF)-alpha , and C-reactive protein (C-RP) | 10                    | x                             | x | x  | x  | Creatinine collected at baseline for those without measure in preceding 2 years.  |
| --skin carotenoids, Reflection Spectroscopy Device ("Veggie Meter"™)   | 5                     | x                             | x | x  | x  |   |
| Questionnaires:   |                       |                               |   |    |    | These data collected before the actual visit, on-line via REDCap or by phone. Window before baseline visit is 4 weeks. Window before follow-up at 4 months is 2 weeks. Window before follow-up visits at 12 and 24 months is 4 weeks. |
| --Demographics, literacy screener  and medical history (baseline only)  | 15                    | x                             |   |    |    |   |
| --Diet assessment: diet quality ,  fat quality ,  adapted PREDIMED checklist   | 10                    | x                             | x | x  | x  |   |
| --Detailed assessment of diet quality: Willett Food Frequency Questionnaire   | 20-30                 | x                             | x | x  | x  |   |
| --Physical activity and sedentary behaviors: GPAQ for physical activity and sedentary behavior ,  participant   | 5                     | x                             | x | x  | x  |   |

| report of monitored steps  |      |   |   |   |   |   |
|--|------|---|---|---|---|---|
| --Quality of life (EQ5D  )  | 5    | x | x | x | x |   |
| --Food insecurity  and material need insecurities    | 8    | x |   |   |   |   |
| --Predictors of behavioral change  |      |   |   |   |   |   |
| --Exercise self-efficacy,  weight loss self-efficacy,  self-regulation,  eating behaviors,  and self-weighing behaviors  | 30   | x | x | x | x |   |
| --Medications for high BP, high blood lipids, diabetes, and weight loss (self-report with EHR review)  | 5    | x | x | x | x |   |
| --Adverse outcomes, CVD events, ER visits, and hospitalizations (follow-up only)   | 5    |   | x | x | x |   |
| --Acceptability (follow-up only)   | 5-10 |   | x | x | x |   |
| Diet and PA goals and success achieving goals (collected by web-based intervention platform)   | NA   |   |   |   |   | Collected after each counseling session in intervention group.  |
| Exploratory Outcome   |      |   |   |   |   |   |
| Stool microbiome (participants may elect not to complete this measure)   | NA   | x | x | x | x | First sample will be collected in the 2 week period immediately after randomization. (These are the only baseline data collected after randomization.) The follow-up samples will be collected w/n a 2 week window of follow-up visit date. |
| Other   |      |   |   |   |   |   |
| --EHR to assess/confirm adverse health outcomes  | NA   |   | x | x | x | To confirm information collected by questionnaire at these visit time points  |
